9.7. MELD Score

For Arm 4, the MELD score will be calculated as follows:

$$\text{MELD Score} = 9.57 \times \ln(\text{creatinine mg/dL}) + 3.78 \times \ln(\text{total bilirubin mg/dL}) + 11.2 \times \ln(\text{INR}) + 6.43$$

The MELD Na Score will be calculated as follows:

$$\text{MELD Na Score} = \text{MELD} - \text{Na (mEq/L)} - [0.025 \times \text{MELD} \times (140 - \text{Na (mEq/L)})] + 140$$

For calculation of the MELD score, laboratory values less than 1.0 will be set to 1.0 and serum creatinine values greater than 4.0 mg/dL (equivalent to 353.6 $\mu\text{mol/L}$) will be set to 4.0. For calculation of the MELD Na score, sodium (Na) values greater than 140 mEq/L will be set to 140 and values less than 125 mEq/L will be set to 125.

For Arm 4, absolute change from baseline 1 in MELD score will be presented for the Safety Analysis Set. Similar summary tables presenting absolute change from baseline 2 for the 12-week treatment period will be presented for MELD scores for patients in the Safety Analysis Set who actively entered 12-Week treatment period. Supporting listing will also be presented for the Safety Analysis Set.

9.8. Endoscopic biliary dilation intervals/frequency

For Arm 4, a summary table of endoscopic biliary dilation intervals/frequency will be presented for the Safety Analysis Set. The absolute and relative change in the 12 weeks prior to single dosing (V2) compared to the 12-week treatment period (V7) table will also be presented for the Safety Analysis Set. Baseline 1 is defined as data collected on the day of the planned single dose, which are assessments of 12 weeks prior to Single Dosing. Supporting listing will also be presented for the Safety Analysis Set.

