5.2.2 PSC with Clinically Relevant Stricture

Strictures are a common radiographic finding in PSC. Dominant strictures are defined as a biliary stricture observed on ERCP with a diameter of ≤ 1.5 mm in the common bile duct or of ≤ 1 mm in the hepatic duct with further delineation in the definition as a high-grade stricture when there is a $> 75\%$ reduction in the common bile duct on magnetic resonance imaging (MRI) ([Bowlus et al., 2023](#)). A clinically relevant stricture is a high-grade biliary stricture on imaging in the common bile duct or hepatic ducts with signs or symptoms of obstructive cholestasis and/or bacterial cholangitis. A clinically relevant stricture is a high-grade biliary stricture on imaging in the common bile duct or hepatic ducts with signs or symptoms of obstructive cholestasis and/or bacterial cholangitis. Forty (40) to 58% of patients with PSC will develop radiographically apparent strictures ([Aljiffry et al., 2011](#)) and

in 15 to 20% of patients with PSC ([Hilscher et al., 2018](#)), a localized CRS is the most prominent feature at diagnosis. Individuals with CRS may be considered a different population in PSC and could be stratified as a cohort separate from those who do not have CRS. The presence of an untreated CRS, even in the absence of bile duct malignancy, has been associated with more advanced liver disease histologically, increased liver stiffness assessment via Fibroscan, facilitation of bacterial colonization, increased risk for cholangiocarcinoma, significantly reduced survival, and, if the stricture is accompanied by high-grade dysplasia, earlier liver transplantation should be considered ([EASL, 2022](#)).

Patients with CRS's are often excluded from PSC clinical trials, especially if a biliary intervention (stent, dilatation) has occurred within the 3 months prior to the Screening Visit. Clinically relevant strictures are typically managed by endoscopic or surgical interventions such as stenting, or dilatation, or resection. These procedures are not without risk and can include recurrent bleeding, infection, bacterial cholangitis, perforation, or pancreatitis. Balloon dilatations of CRS usually need to be repeated at intervals of 1 to 4 weeks; there is no consensus agreement on dilation protocols; and no results are reported in clinical or biochemical improvement after repeat dilations ([EASL, 2022](#); [European Society of Gastrointestinal et al., 2017](#)).

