6.2.3 Exploratory Endpoints

The exploratory endpoints are:

- Change from Baseline to Week 12 in autotaxin
- Change from Baseline to Week 12 in ProC3
- Change from Baseline to Week 12 in high-sensitivity C-reactive protein (hsCRP)
- Change from Baseline to Week 12 in matrix metalloprotease 7(MMP7) and matrix metalloprotease 9 (MMP9)
- Change from Baseline to Week 12 in enhanced liver fibrosis (ELF) and Mayo-PSC score
- Change from Baseline to Week 12 in carbohydrate antigen 19-9 (CA 19-9)
- Change from Baseline to Week 12 in liver stiffness as assessed by FibroScan
- Change from Baseline to Week 12 in pruritus using the daily pruritus scores captured via the Pruritus Numerical Rating Scale (NRS)
- Change from Baseline to Week 12 in fatigue using the daily fatigue scores captured via the fatigue NRS
- Change from Baseline to Week 12 in sleep disturbance using the daily sleep disturbance scores captured via the sleep disturbance NRS
- Change from Baseline to Week 12 in mood using the daily mood scores captured via the mood Likert scale
- Episodes of cholangitis requiring antibiotic use in the 12 weeks prior to dosing versus the 12 weeks after dosing

Additional Exploratory Endpoints, Arm 4 Only

- Change of model for end-stage liver disease (MELD) score from baseline to Week 12
- Change in endoscopic biliary dilation intervals/ frequency in the 12 weeks prior to study start (V2) compared to the 12-week treatment period for those subjects who are regularly dilated.

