3.2.3. Exploratory Endpoints

The exploratory endpoints are:

- Change from Baseline to Week 12 in autotaxin
- Change from Baseline to Week 12 in ProC3
- Change from Baseline to Week 12 in high-sensitivity C-reactive protein (hsCRP)
- Change from Baseline to Week 12 in matrix metalloprotease 7 (MMP7) and matrix metalloprotease 9 (MMP9)
- Change from Baseline to Week 12 in enhanced liver fibrosis (ELF) and Mayo-PSC score
- Change from Baseline to Week 12 in carbohydrate antigen 19-9 (CA 19-9)
- Change from Baseline to Week 12 in liver stiffness as assessed by FibroScan
- Changes from baseline to Week 12 in pruritus using the daily pruritus scores captured via the pruritus numerical rating scale (NRS)
- Change from Baseline to Week 12 in fatigue using the daily fatigue scores captured via the fatigue NRS
- Change from Baseline to Week 12 in sleep disturbance using the daily sleep disturbance scores captured via the sleep disturbance NRS
- Change from Baseline to Week 12 in mood using the daily mood scores captured via the mood Likert scale
- Episodes of cholangitis requiring antibiotic use in the 12 weeks prior to single dosing versus the 12 weeks after dosing

Additional exploratory endpoints, Arm 4

- Change of model for end stage liver disease (MELD) from baseline to Week 12
- Change in endoscopic biliary dilation intervals/ frequency in the 12 weeks prior to single dosing (V2) compared to the 12-week treatment period for those patients who are regularly dilated.

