4.3.3. Safety Analysis Set

The safety analysis set will include all patients who received at least 1 dose of A3907 and will be used for all analyses except PK and PD analyses.

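### SAP 9.8 does not apply the endpoint's limit to regularly dilated patients, and its interval summary, if intervals are taken within a period, loses the patients who improve most

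*SAP*

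**What the plan says.** The endpoint compares dilation intervals/frequency in the 12 weeks before the single dose with the treatment period, in Arm 4 only. Both endpoint lists restrict the population. Protocol 6.2.3 refers to the "12-week treatment period for those subjects who are regularly dilated". SAP 3.2.3 has the same limit: "compared to the 12-week treatment period for those patients who are regularly dilated".

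SAP 9.8 specifies the analysis without that limit: "For Arm 4, a summary table of endoscopic biliary dilation intervals/frequency will be presented for the Safety Analysis Set". It adds "The absolute and relative change in the 12 weeks prior to single dosing (V2) compared to the 12-week treatment period (V7) table", also for the Safety Analysis Set. SAP 4.3.3 defines that set by dosing alone: "The safety analysis set will include all patients who received at least 1 dose of A3907". The baseline data are those of the look-back, "which are assessments of 12 weeks prior to Single Dosing".

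SAP Table 2 gives endoscopic dilation data an on-treatment window that opens after baseline and closes 7 days after the last dose day (or the end-of-treatment visit day, if later). SAP 11, which lists changes from the protocol, mentions nothing on this endpoint.

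Neither document defines interval, frequency or regularly dilated, or says what is done when a period holds 0 or 1 dilations. On usual practice, protocol 5.2.2 says: "Balloon dilatations of CRS usually need to be repeated at intervals of 1 to 4 weeks".

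**The concern.** There are three linked problems.

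- **Population.** The Arm 4 entry criteria require a clinically relevant stricture, not a history of dilation. A table over all of Arm 4 can therefore include patients with no dilation in the look-back. They pull the mean absolute change towards zero, and their relative change does not exist.
- **Interval.** Interval and frequency move in opposite directions and behave differently at low counts. A count of 0 or 1 is a valid frequency, but a gap within one period needs two dilations. Under that reading, the interval summary drops patients because they improved.
- **Observation time.** If the Table 2 window selects the dilations, the on-treatment count covers more days than the look-back count.

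This is the only endpoint listed for the Arm 4 objective on bile duct function. With about six patients, one or two included or lost change the summary visibly.

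**Working it through.** The plan gives no figure for this endpoint, so there is none to reproduce. The inputs are a 12-week (84-day) look-back and a 12-week treatment period (SAP 9.8), the SAP Table 2 window, six patients in Arm 4 (SAP 4.1) and usual spacing of 1 to 4 weeks (protocol 5.2.2). On-treatment spacing is not given, so it is varied as an assumption.

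**1. Length of the Table 2 window.** Protocol Day 98 is Day 99 in the SAP's numbering. The window runs from Day 2 to Day 99 + 7 = Day 106, which is 105 days. 105/84 = 1.25, so it is 25% longer than the look-back.

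**2. Effect on raw counts.** At an unchanged 4-week spacing, the expected count is 84/28 = 3 before dosing and 105/28 = 3.75 on treatment, an apparent rise of 0.75 with no true change. A true fall of 20% in the rate would show as no change, since 1.25 × 0.80 = 1.

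**3. Zero-baseline patients.** If k of 6 patients go from zero to zero, the mean absolute change is multiplied by (6 − k)/6: 0.83 for k = 1, 0.67 for k = 2 and 0.50 for k = 3. Relative change for these patients is 0/0, or a positive number over 0 if they are dilated on treatment. The value of k is an assumption.

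**4. Share of patients with a within-period interval.** At the usual spacing of 1 to 4 weeks, an 84-day look-back holds 12 to 3 dilations, so a baseline interval exists. On treatment, take regular spacing of L days with a random starting phase in a window of W days. The chance of at least two dilations is 1 if 2L ≤ W, (W − L)/L if W/2 < L < W, and 0 if L ≥ W.

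| Spacing L (days) | W = 84 | W = 105 |
|---|---|---|
| 28 | 100% | 100% |
| 42 | 100% | 100% |
| 49 | 35/49 = 71% | 100% |
| 56 | 28/56 = 50% | 49/56 = 88% |
| 63 | 21/63 = 33% | 42/63 = 67% |
| 70 | 14/70 = 20% | 35/70 = 50% |
| 84 | 0% | 21/84 = 25% |

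If spacing doubles from 4 to 8 weeks, about 3 of 6 patients (84 days) or 5.25 of 6 (105 days) would have an interval, assuming all six are regularly dilated. Doubling from 1, 2 or 3 weeks gives 2, 4 or 6 weeks, and none is lost in either window.

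**5. Irregular dilations.** With a Poisson count of mean m per 12 weeks, the chance of fewer than two is exp(−m)(1 + m): 0.20 at m = 3, 0.41 at m = 2 and 0.74 at m = 1. Of six patients, about 1.2, 2.4 and 4.4 would have no interval. The loss grows as the dilation rate falls, in line with step 4.

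**6. The count at the same extremes.** A fall from 3 dilations to 0 gives an absolute change of −3 and a relative change of −100%. Nobody is lost from the frequency summary for improving.

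**The case against.** The strongest reply is that the measure is intervals/frequency, and frequency already captures the best outcomes. That stands. A reader might infer that patients who improve most cannot be scored on the endpoint at all. The documents do not support this, because such patients are missing only from the interval part.

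A reader might also infer that the SAP requires two dilations within 12 weeks, or that no interval above 84 days could be recorded. Neither document says so. A gap running from the last pre-dose dilation is not ruled out, since dilation data are documented at Visits 1, 2 and 7. The within-period reading is natural because SAP 9.8 compares one period with another, but it remains a reading. The missing definition is itself a gap, because the choice would be made with open-label data in view.

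Nor has the SAP abandoned the restriction. SAP 3.2.3 keeps it, and only 9.8 fails to repeat it. This is an internal inconsistency, and applying the restriction in 9.8 would largely remove the dilution and zero-denominator problems.

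Finally, the number of patients is shown with every summary and 9.8 provides a listing, so missing intervals would be visible. That is fair and limits the harm, but it does not say which patients the table should contain.

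**Conclusion.** The point holds in limited form. SAP 9.8 as written analyses a wider population than the endpoint names. That allows zero-to-zero changes and undefined relative changes. If intervals are taken within a period, their summary alone loses the patients who improve most. At 8-week spacing, about 50% have an interval in an 84-day window and about 88% in the Table 2 window. If the Table 2 window selects the data, raw on-treatment counts also cover 25% more time than the look-back, which works against the drug.

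The percentages rest on regular spacing with random phase and on the within-period reading. There is no loss while on-treatment spacing is 6 weeks or less. The 25% assumes a last dose on SAP Day 99. Severity is minor: the endpoint is exploratory, descriptive and uncontrolled, in about six patients, and no test or decision rule depends on it.

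**What to change.** In SAP 9.8 and the related tables:

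- Make the main measure the number of dilations per 84 days of observation in each period, with zero a valid value.
- Restrict the change table to regularly dilated Arm 4 patients and state the definition. The documents give none, so the sponsor must choose. At least one dilation in the 12 weeks before Visit 2 is one example, and it makes relative change defined for everyone in the table.
- Keep intervals as a secondary display or listing. Define them, and report how many patients had fewer than two dilations in each period.
- Align the Table 2 window for dilation data with the 12-week treatment period.
- Record any demotion of the interval measure in SAP 11, since the protocol names intervals in the endpoint.

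The cost is SAP wording and a less prominent mean-interval display. Aligning the window assumes that dilation dates are recorded, which the documents do not state.

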9.9. Liver stiffness

Liver stiffness will be assessed by FibroScan. Fibroscan will be performed as per institution standard practice where available. The data collected on the Fibroscan form (liver stiffness measured in kPa) will be converted to determine stage of fibrosis on a 0 to 4 scale, using below score card based on grading from the study that looked at liver stiffness measurements (LSM) and association with degree of fibrosis in patients with PSC ([Corpechot 2014](#)) as outlined in Table 3.

Table 3: Fibroscan Scoring (Fibrosis Stage)

STAGE	F0 NO FIBROSIS	F1 PORTAL FIBROSIS WITHOUT SEPTA	F2 PORTAL AND PERIportal FIBROSIS WITH FEW SEPTA	F3 PORTAL AND PERIportal FIBROSIS WITH NUMEROUS SEPTA WITHOUT CIRRHOSIS	F4 CIRRHOSIS
Liver stiffness measurement by Fibroscan	<7.4 kPa	≥7.4 to <8.6 kPa	≥8.6 to <9.6 kPa	≥9.6 to <14.4 kPa	≥14.4 kPa

Relative and absolute change from baseline 1 in Fibroscan results will be presented for the Safety Analysis Set. Similar summary tables presenting relative and absolute change from baseline 2 for the 12-week treatment period will be presented for Fibroscan results for patients in the Safety Analysis Set who actively entered 12-Week treatment period. A listing of liver stiffness will also be presented for the Safety Analysis Set. The frequencies of stages may be summarised by frequency tables.

9.10. Mayo PSC-score

The Mayo PSC score will be calculated as follow:

$$R = 0.03 (\text{age [y]}) + 0.54 \log_e (\text{bilirubin [mg/dL]}) + 0.54 \log_e (\text{aspartate aminotransferase [U/L]}) + 1.24 (\text{variceal bleeding [0/1]}) - 0.84 (\text{albumin [g/dL]}).$$

Where R is the Risk Score.

Absolute change from baseline 1 in Mayo PSC Score will be presented for the Safety Analysis Set. Similar summary tables presenting absolute change from baseline 2 for the 12-week treatment period will be presented for Mayo PSC Score for patients in the Safety Analysis Set who actively entered 12-Week treatment period. A listing of Mayo PSC Score will also be presented for the Safety Analysis Set.

9.11. Numerical Rating Score Assessments

The scoring of NRS will range from 0 (“No itch”) to 10 (“worst imaginable itch”). This will be interpreted as follows:

- NRS = 0 – No Pruritus
- NRS < 3 – Mild Pruritus
- NRS ≥ 3<7 – Moderate Pruritus
- NRS ≥ 7<9 – Severe Pruritus
- NRS ≥ 9 – Very Severe Pruritus

These scores will be used for Pruritus, Fatigue and Sleep Disturbance.

For Patient Diary Reviews (Pruritus NRS, Fatigue NRS, Sleep Disturbance NRS, Mood Likert Scale), the weekly, biweekly and monthly score will be calculated as in [Appendix 3](#) based on each period. The following assessments will be presented at each weekly, biweekly and monthly period. Baseline 1 will be calculated by averaging the two-baseline weekly score in the 14 days preceding the planned single dose. The single treatment period score is calculated by averaging the weekly scores in the 14 days of single treatment period of planned single dose. For biweekly and monthly score summary, single treatment period of planned single dose will be included as the first post-baseline period; 2-week safety follow-up period will be presented as the last post-baseline period.

9.11.1. Daily Pruritus Score

Pruritus NRS will be completed in the patient diary only for patients that report experiencing pruritus at the Screening Visit. The summary table and relative and absolute change from baseline 1 in pruritus derived using the Pruritus NRS will be presented for the Safety Analysis Set. A listing of daily pruritus score will also be presented for the Safety Analysis Set.

9.11.2. Fatigue Score

The summary table and relative and absolute change from baseline 1 in fatigue score derived using the Fatigue NRS will be presented for the Safety Analysis Set. A listing of Fatigue score will also be presented for the Safety Analysis Set.

9.11.3. Sleep disturbance Score

The summary table and relative and absolute change from baseline 1 in sleep disturbance score derived using the sleep disturbance NRS will be presented for the Safety Analysis Set. A listing of sleep disturbance score will also be presented for the Safety Analysis Set.

9.11.4. Mood Scale

Mood Likert scale data collected in the patient diary will be converted to numerical scores using below criteria:

- Never – 0
- Almost never – 1
- Sometimes – 2
- Often – 3
- Always – 4

The summary table of mood Likert scales and relative and absolute change from baseline 1 in mood scores using above criteria will be presented for the Safety Analysis Set. A listing of mood scales will also be presented for the Safety Analysis Set.

9.12. Pregnancy

Serum pregnancy test will be performed for all women upon Screening. For women of childbearing potential (WOCBP), urine pregnancy test will be done at Visit 2 through Visit 8. A point of care urine dipstick for pregnancy will be obtained. If the results are positive for pregnancy, a human chorionic gonadotropin (hCG) blood pregnancy test will be performed. A Patient listing of pregnancy test results will be provided.

10. Interim Analysis/Other Analysis

10.1. Interim Analysis

An interim analysis may be conducted. This analysis will be triggered by ongoing review of data and need for communication with regulatory authorities/agencies. Additional analyses may be performed at selected time points throughout the collection of patient data for regulatory requirements and sponsor decision making purposes.

10.2. Safety Review Committee

An SRC will be established for Study A3907-002 which may consist of the sponsor, and the lead investigator (as detailed in the SRC charter). The SRC will review safety and PK data after at least three (3) patients have completed two (2) weeks of treatment in Arm 1 to determine if enrolment in Arm 2 may occur. The SRC will review safety and PK data after at least three (3) patients have completed two (2) weeks of treatment in Arm 2 to determine if enrolment in Arms 3 and 4 may occur. The SRC will also meet periodically for the review of accumulating study data, including safety (AE and laboratory data), until the last patient reaches 12 weeks.

The SRC will make recommendations for the remaining part of the study. The SRC may recommend continuing with the study as planned or stopping the study early for safety reasons. The investigators (or designees) will only be informed by the sponsor or designee if the study requires a protocol amendment or is stopped. The SRC may choose to make additional evaluations at any time if they feel this is warranted from a safety point of view.

10.3. Coronavirus Pandemic

In accordance with guidance issued by regulatory agencies, study data collection will document visits missed due to COVID-19 related reasons and assessments completed via alternative method due to COVID-19 related reasons.

The COVID-19 impacts on individual patients collected on the COVID-19 eCRF pages will be listed for the Enrolled Set. Protocol deviations related to COVID-19 will be indicated in the protocol deviation listing for the Enrolled Set.

The anticipated impact of COVID-19 is widely regarded as unknown. If the impact of COVID-19 on the conduct of this study is observed to be significant, further summaries and listings of the impact will be explored.

11. Changes in the Planned Analysis from Study Protocol section

Day 0 in the protocol has been updated to Day 1 in SAP.

The protocol contains different statistical analysis sets, Screened Set and Enrolled Set were added in the SAP to support disposition analysis and supporting listings.

MIST analysis will not be conducted.

Laboratory clinical significance determined by the investigator's discretion is not available and will not be presented in the analysis. However, laboratory toxicity and its CTCAE grades will be included in the listings.

12. Reference

13. Appendices

13.1. Appendix 1: Imputation Algorithm for Partial and Missing Dates

13.1.1. Rules for AE Start Date Imputation

The following rules will be applied to impute the missing numerical fields.

Missing day and month

- If the year of the incomplete start date is the same as the year of the date of the first dose of study drug and the end date is on or after the first dose of study drug, then the day and month of the date of the first dose of study drug will be assigned to the missing fields.
- If the year of the incomplete start date is the same as the year of the date of the first dose of study drug and the end date is prior to the first dose of study drug, then 01 January will be assigned to the missing fields.
- If the year of the incomplete start date is different from the year of the date of the first dose of study drug, then 01 January will be assigned to the missing fields.

Missing month only

- The day will be treated as missing and both month and day will be replaced according to the above procedure.

Missing day only

- If the month and year of the incomplete start date are the same as the month and year of the date of the first dose of study drug and the end date is on or after the first dose of study drug, then the day of the date of the first dose of study drug will be assigned to the missing day.
- If the month and year of the incomplete start date are the same as the month and year of the date of the first dose of study drug and the end date is prior to the first dose of study drug, then the first day of the month will be assigned to the missing day.
- If the month and year are different from the year of the date of the first dose of study drug, then the first day of the month will be assigned to the missing day.

Missing year

- If the year of AE start is missing or AE start date is completely missing, then query the site with no imputation.

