3.1. Overall Study Design and Plan

This is an open-label, Phase 2 study to evaluate the safety, tolerability, PK, and PD effects of three (3) dose levels of A3907, 10 mg (Arm 1), 30 mg (Arm 2) administered orally once daily (QD), or 30mg twice daily (BID) in Arms 3 and 4 for 12 weeks in patients with PSC with and without CRS ([Figure 1](#)). Eligible patients must have a clinical diagnosis of large-duct PSC obtained by appropriate biliary imaging, and evidenced by chronic cholestasis of more than 6 months duration. Patients must also have serum bile acids above the upper limit of normal (ULN) at Screening Visit and alkaline phosphatase (ALP) levels $> 1.5 \times$ ULN but $\leq 10 \times$ ULN repeated at least 2 weeks apart for baseline to reflect variability of $< 30\%$. If variability is $> 30\%$, a third ALP level may be obtained to determine the direction of abnormality or document stability. If stable ($< 30\%$ variance) the patient may be enrolled.

Prior to any other study procedures being conducted, the patient will have the nature of the study explained to him/her and be asked to sign an informed consent form (ICF). Informed consent must be obtained prior to any study procedures that do not form a part of the patient's normal care. After signing the ICF, patients will be evaluated for study eligibility. If not fasting at time of consent, patient will return to complete screening assessments after having fasted for 4 hours.

The study will include up to a 2-week Screening Period, followed by administration of a single dose of A3907, followed by a 2-week period to confirm the target exposure is reached before beginning a treatment period of 12 weeks ([Figure 1](#)). There will be a total of 8 scheduled visits during the study (including 1 Screening Visit).

Figure 1: Study Design

*EASL defined MRCP Equivalent of clinically relevant strictures: A biliary stricture on MRI/MRCP with > 75% reduction of duct diameter in the common bile duct or hepatic ducts
BID = twice daily; f/u = follow up; PK = pharmacokinetic; QD = once daily; wks = weeks; EASL = European Association for the Study of the Liver

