4.1. Sample Size

Due to the exploratory nature of this study, no formal power calculations will be used to determine sample size. Approximately 24 patients will be enrolled with six (6) patients in each treatment arm. To ensure 6 patients are enrolled into the 12-week Treatment Period of each treatment arm, patients that discontinue due to an adverse event, withdrawn or terminated early patients may be replaced as needed.

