4.4. Study Day

Study Day 1 is defined as the date of first single dose. The reference date for the calculation of study days will be Study Day 1. For some analysis purposes, study day is calculated as:

Date of assessment – Day 1 +1, for assessments done after first dose of study drug;

Date of assessment – Day 1, for assessments done before the first dose of study drug.

The screening period for the study will be from Day -14 (± 2) to Day 1. The single dose will be administered on Day 1/Visit 2. The 12-week treatment period will be from Visit 3 to Visit 7. The End-of-Study Visit will occur on Visit 8.

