A patient with multiple AEs within a primary SOC or PT will only be counted once towards the total for that SOC and/or PT. For the AE severity and relationship summaries, if a patient reported more than one AE with the same PT, the AE with the greatest severity or relationship will be presented. For table summaries if severity is missing then 'Grade 3 (Severe)' is assumed. For the purposes of summarising AEs related to study drug, a relationship of 'possibly related', 'probably related' or 'definitely related' will be considered as related to the study drug. A relationship of 'not related' or 'unlikely related' will be considered as not related to the study drug. If relationship is missing, relationship to study drug is assumed to be 'related'. AEs with a

toxicity grade of greater than or equal to grade 3 will be considered as severe adverse events. Summaries of TEAEs will be presented separately by the single dose (Day 1 to Day 14), 12-week (Day 15 to Day 112) and overall treatment periods by treatment arm and overall.

Following patient listings will be provided based on the safety analysis set.

- TEAEs
- SAEs
- Drug-related AEs
- AEs leading to treatment discontinuation
- AEs leading to treatment interruption
- AEs leading to study discontinuation
- Deaths

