13.1.2. Rules for AE End Date Imputation

Incomplete stop dates will not be imputed.

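### Partial AE start dates are imputed from the single-dose date alone, so events of uncertain day in the month 12-week dosing starts are nearly all booked to the single-dose period

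*SAP*

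**What the plan says.** SAP 4.4 fixes the time origin: "Study Day 1 is defined as the date of first single dose". According to SAP 3.1 the single dose is "followed by a 2-week period to confirm the target exposure is reached before beginning a treatment period of 12 weeks". Every start-date rule in SAP 13.1.1 is tied to the first dose of study drug:

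- Day missing, same month and year as first dose, event ended on or after first dose: "then the day of the date of the first dose of study drug will be assigned to the missing day".
- Day missing, same month and year, event ended before first dose: the 1st of the month.
- Day missing, other month: "If the month and year are different from the year of the date of the first dose of study drug", the 1st of the month is used. The wording compares a month and year with a year only, which is a slip.
- Day and month missing: the single-dose date if the year matches and the event ended on or after first dose, otherwise 01 January.

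No rule mentions the first dose of the 12-week period. On end dates, SAP 13.1.2 says: "Incomplete stop dates will not be imputed".

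SAP 9.1 then needs each event assigned to a period: "Summaries of TEAEs will be presented separately by the single dose (Day 1 to Day 14), 12-week (Day 15 to Day 112", and also overall. Protocol 10.2.2.5 requires the same split with its own day numbering (Day 0 to 13, Day 14 to 112).

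**The concern.** The algorithm answers whether an event began after any study drug. It does not answer whether it began after repeat dosing started, and the period tables need that second answer. The default always pulls the onset back, to the single dose or to the start of a month, so the error runs in one direction: from the repeat-dose table into the table for one dose. The primary objective concerns safety after repeat doses, so the 12-week table is the one most readers will turn to, and it is the one that loses events.

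**Working it through.** The plan states no figure on this point, so there is none to reproduce. The check applies the SAP 13.1.1 rules to the calendar.

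**Inputs.** First dose is SAP Day 1 (SAP 4.4). 12-week dosing starts nominally on SAP Day 15, because protocol Day 14 becomes SAP Day 15 after the relabelling in SAP section 11. The ±2-day Visit 3 window in the protocol's schedule of assessments gives SAP Day 13 to 17. The period boundary is Day 14/15 (SAP 9.1).

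**Assumptions.** First-dose dates are spread evenly over 2022 to 2025 (1,461 dates, 48 months). The event did not end before first dose. Only the day is missing, and the recorded month is the one in which 12-week dosing starts.

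**Where the imputed date falls, Day 15 start**

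- The 12-week start falls on the 15th or later. The single dose is then in the same month, and the imputed date is Day 1, always in the single-dose period. Share: (1,461 − 48 × 14) / 1,461 = 789 / 1,461 = 54.0%.
- It falls on the 1st to the 14th. The single dose is then in the previous month, and the imputed date is the 1st. Share: 672 / 1,461 = 46.0%. The 1st precedes the 12-week start unless dosing starts on the 1st itself.
- The exception is 48 / 1,461 = 3.3%. Booked to the single-dose period: 1 − 0.033 = **96.7%**.

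**Visit window, fixed Day 15 boundary**

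| 12-week start (SAP day) | Start dates that escape | Booked to single dose |
|---|---|---|
| 13 or 14 | none | 100% |
| 15 | start on the 1st: 48 / 1,461 | 96.7% |
| 16 | 1st or 2nd: 96 / 1,461 | 93.4% |
| 17 | 1st to 3rd: 144 / 1,461 | 90.1% |

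If the boundary is the actual first 12-week dose, the figure is 96.7% throughout.

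**Where such events could truly lie.** Count the days in that month on or after first dose, pooled over all start dates. Of these, 22,981 fall in the 12-week period and 15,414 in the single-dose period. The 12-week share is 22,981 / 38,395 = 59.9%. Averaged over start dates instead of pooled over days, it is 55.3%. With onset days taken as uniform, 93.6% of the true 12-week onset days in that month are booked to the single dose.

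**Example.** Single dose 5 March, 12-week dosing from 19 March, true onset 28 March recorded only as March, event ended after first dose. The rule assigns 5 March, Day 1.

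**Over the whole 12-week period.** Across all onset days from Day 15 to 112, 15.0% are misplaced if only the day is missing, and 86.4% if day and month are both missing.

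**Effect on a rate.** With six patients per arm (SAP 4.1), one patient moved changes a period-specific incidence by 1 / 6 = 16.7 points at most.

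**The case against.** Imputing to first dose protects against losing a TEAE, and for that purpose the rule works. A reader might infer that the primary endpoint is biased. The documents do not support that. Both imputed dates are on or after first dose, so a dated post-dose event stays a TEAE and stays in the overall table and the TEAE listing; only its place in the two descriptive sub-tables changes. This part of the objection stands in full.

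A reader might also take 97% as an expected error rate. It is conditional on a partial date in one particular calendar month. The documents do not say how many AEs have partial dates. AEs are recorded at all eight visits and protocol 12.2 asks for query responses within 3 working days, so the number may be small.

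Nor does each moved event shift a rate by 17 points. SAP 9.1 counts a patient once per SOC or PT, so the 12-week rate falls only if that patient has no other event in the same row in that period. Replacement of patients can also take the safety set above six per arm.

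Finally, the same-month and same-year rules literally cover only an end date on or after, or before, first dose. It is tempting to say that an ongoing event therefore has no TEAE status. An event still ongoing during the study has plainly not ended before first dose, so the on-or-after branch is the natural reading. What remains is a wording gap.

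None of this removes the one-directional misplacement between the period tables.

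**Conclusion.** The point holds as a narrow one. SAP 13.1.1 lacks the date that the SAP 9.1 period split needs, and for a missing day in the month 12-week dosing starts it chooses the single-dose period almost regardless of the calendar: 96.7% nominally, 90.1% to 100% within the visit window. If Visit 3 slips beyond its window the share falls under the fixed boundary, for example to 73.7% for a Day 22 start. These figures rest on evenly spread start dates; the share of true 12-week onsets misplaced also assumes uniform onset days. The absolute effect cannot be sized without the count of partial dates. The study is descriptive and the overall incidence is safe, so this is worth correcting because it is cheap. It does not threaten the main conclusion.

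**What to change.** In SAP 13.1.1:

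1. For period assignment only, add the first 12-week dose date as a second anchor. Apply it when the partial date is compatible with that dose's month (or year, if the month is also missing) and the event is ongoing or ended on or after that dose.
2. Flag these events in the listing and show the period tables under both assignments, or give them a row for period undetermined.
3. State that a missing or ongoing end date counts as on or after first dose.
4. Correct the clause that compares a month and year with a year.

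Step 2 is needed because the second anchor used alone reverses the error. It places all true 12-week onsets in that month correctly, but 15,414 / 38,395 = 40.1% of the possible post-dose days (100 − 55.3 = 44.7% averaged over start dates) belong to the single-dose period. Events from those days would move the other way if ongoing or ended on or after the 12-week start. Because the second date serves only the period tables, the flag also explains any difference between tables and listings.

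Cost: a few SAP sentences and some extra table programming, with no change to design or data collection.
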